#### 5. RESOURCES AVAILABLE TO CONDUCT THE HUMAN RESEARCH

- Explain the feasibility of meeting recruitment goals of this project and demonstrate a potential for recruiting the required number of suitable subjects within the agreed recruitment period
  - How many potential subjects do you have access to?
- Describe your process to ensure that all persons assisting with the trial are adequately informed about the protocol and their trial related duties and functions

The recruitment goals will be met by enrolling patients from the fertility clinic at the point of care. The accrual goal is 30 participants but we may enroll up to 50 participants. Potentially we have access to 2000 patients.

After IRB approval is obtained, we will have a site initiation meeting to ensure that all study personnel are informed of the process for recruiting subjects, and how the study procedures will be conducted in addition to a detailed review of the study protocol.

#### 6. RECRUITMENT METHODS

- *Describe the source of potential subjects*
- Describe the methods that will be used to identify potential subjects
- Describe any materials that will be used to recruit subjects. A copy of any advertisements (flyers, radio scripts, etc.) should be submitted along with the protocol.
- If monetary compensation is to be offered, this should be indicated in the protocol

We are aiming to recruit 30 patients from the Northwell fertility clinic at the point of care for their infertility work-up. The clinicians in this study will see the potential subjects in their routine clinical care.

The physicians in the Department of Radiology and Northwell Health Fertility will play the dual role of clinician and research investigator.

#### 7. ELIGIBILITY CRITERIA

- Describe the characteristics of the subject population, including their anticipated number, age, ranges, sex, ethnic background, and health status. Identify the criteria for inclusion or exclusion of any subpopulation.
- Explain the rationale for the involvement of special classes of subjects, such as fetuses, pregnant women, children, prisoners or other institutionalized individuals, or others who are likely to be vulnerable. You cannot include these populations in your research, unless you indicate such in the protocol
- Similarly, detail exclusionary criteria: age limits, special populations (minors, pregnant women, decisionally impaired), use of concomitant medications, subjects with other diseases, severity of illness, etc.

#### Inclusion Criteria:

- All women undergoing evaluation for infertility greater than 6 months in the Northwell health system
- Non-pregnant Women Age 18-50
- Diagnosis of male infertility
- Diagnosis of ovulatory dysfunction
- Diminished ovarian reserve, unexplained
- Recurrent pregnancy loss

#### Exclusion Criteria:

- History of active pelvic infection
- History of tubal ligation or salpingectomy
- History of adverse reaction to iodinated contrast
- Pregnancy

#### 8. NUMBER OF SUBJECTS

- Indicate the total number of subjects to be accrued locally. If applicable, distinguish between the number of subjects who are expected to be pre-screened, enrolled (consent obtained), randomized and complete the research procedures.
- If your study includes different cohorts, include the total number of subjects in each cohort.
- If this is multisite study, include total number of subjects across all sites.

We aim to enroll approximately 30 study subjects. We will go up to enrolling 50 subjects and after this point we will stop enrollment.

#### Sample Size Justification

The proposed sample size of 30 is based on feasibility, availability of resources, and the study timeline and not on any formal statistical power calculations. Once we have determined the feasibility of the sonoHSG, we intend to proceed with a larger clinical trial and appropriately power that study with a larger sample size.

#### 9. STUDY TIMELINES

- Describe the duration of an individuals participation in the study
- *Describe the duration anticipated to enroll all study subjects*
- The estimated date of study completion

Study participants will be enrolled in the study for up to 3 weeks.

We anticipate completing enrollment within 12 months.

The estimated time of study completion is 12 months.

#### 10. ENDPOINTS

- Describe the primary and secondary study endpoints
- Describe any primary or secondary safety endpoints

# Primary Study Endpoint:

Concordance between sonoHSG and HSG results. The sonoHSG and HSG will be considered interchangeable if the level of agreement between them is >= 80%.

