#### 2. BRIEF SUMMARY OF RESEARCH

- The summary should be written in language intelligible to a moderately educated, non-scientific layperson.
- It should contain a clear statement of the rationale and hypothesis of your study, a concise description of the methodology, with an emphasis on what will happen to the subjects, and a discussion of the results.
- This section should be ½ page

This pilot study is a collaborative effort between Northwell Health Fertility and the Radiology Department to streamline the fertility evaluation process and reduce the burden of stress many fertility patients experience by eliminating an imaging examination which is painful and exposes the patient to potentially harmful radiation.

The aim of this study is to improve the workup of infertility by integrating the examination of structural abnormalities of the fallopian tubes and uterus into a single radiation-free ultrasound guided procedure, the sonohysterosalpingogram (sonoHSG). Confirmation of tubal patency is extremely important as approximately 25-35% of female infertility can be attributed to fallopian tube pathology.1 The current paradigm is to use two separate imaging exams; the hysterosalpingogram (HSG), a transvaginal procedure that uses radiation and iodinated contrast to visualize the fallopian tubes, and the sonohysterogram, a transvaginal procedure that uses ultrasound and saline to visualize the uterus. By using agitated saline, to produce air bubbles, fallopian tube visualization is optimized during the time of sonohysterogram (sonoHSG). We plan to also utilize a continuous saline-air device that may produce a technically superior sonoHSG.

As a result of this study, the Radiology Department and Northwell Health Fertility will work together to encourage, educate, and support physicians to promote the utility of sonoHSG as the first imaging examination for the infertility workup. Currently, our institution is not routinely utilizing the sonoHSG despite the advantages in safety, comfort, and convenience to the patient. We aim to effect a change in the current practice at our institution by increasing the knowledge and visibility of the sonoHSG by creating educational materials for referring physicians, and creating a pilot program that demonstrates the value and efficacy of the exam. SonoHSG can be performed concurrently at the time of the sonohysterogram at no additional cost to the patient.

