We will enroll 30 patients from Northwell Health Fertility over the course of one

year. Measures of success will include concordance between sonoHSG and HSG in patients who receive both procedures, and patient surveys evaluating pain utilizing the pain scale. If sonoHSG proves to be efficacious, our future steps will be to educate referring physicians and patients about the utility of the examination using print materials and a grand rounds lecture. We will also measure the number of sonoHSGs ordered compared to HSGs for the evaluation of fallopian tube patency in order to evaluate if there has been a shift in the standard of care.

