The results of the study will be significant in determining and possibly changing the standard of care procedure from HSG to sonoHSG. Currently, the first line examination for the evaluation of fallopian tube patency is the hysterosalpingogram (HSG). This test involves radiation exposure, the use of iodinated contrast, and is accompanied by significant patient discomfort secondary to painful cervical manipulation and at times violent uterine contractions. 4 Some patients also require a sonohysterogram (aka a "water ultrasound") to better evaluate the endometrial lining and to assess for polyps, scar tissue, fibroids, or congenital uterine anomalies that may prevent a successful pregnancy. This initiative will extend the diagnostic capacity of the sonohysterogram by utilizing air bubbles, via a continuous air saline device, to allow concurrent visualization of the fallopian tubes (sonohysterosalpingography). Prior studies have shown, and our experience confirms, that fallopian tube patency can be accurately confirmed by sonoHSG and results are concordant with the HSG.3

The Radiology Department and Northwell Health Fertility will work together to encourage, educate, and support physicians to promote the utility of sonoHSG as the first imaging examination for the infertility workup. Currently, our institution is not routinely utilizing sonoHSG despite the advantages in safety, comfort, and convenience to the patient. We aim to effect a change in the current practice at our institution by increasing the knowledge and visibility of the sonoHSG by creating educational materials for referring physicians, and

creating a pilot program that demonstrates the value and efficacy of the exam. SonoHSG can be performed concurrently at the time of sonohysterogram at no additional cost to the patient.

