#### 4. OBJECTIVE(S)/SPECIFIC AIMS AND HYPOTHESES

- A concise statement of the goal(s) of the current study.
- *The rationale for and specific objectives of the study.*
- The goals and the hypothesis to be tested should be stated.

The specific aim of this study is to evaluate the feasibility of the sonoHSG for it to be determined as the standard of care. Additionally, this is to improve the workup of infertility by integrating the examination of structural abnormalities of the fallopian tubes and uterus into a single radiation-free ultrasound guided procedure, the *sonohysterosalpingogram*.

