#### 12. STATISTICAL ANALYSIS

- *Describe how your data will be used to test the hypotheses.*
- State clearly what variables will be tested and what statistical tests will be used.
- *Include sample size calculations.*
- If this is a pilot study, state which variables will be examined for hypothesis generation in later studies.

Standard methods for descriptive statistics will be used, such as means, medians, proportions, and their associated 95% confidence intervals.

Concordance of the results between sonoHSG and HSG will be calculated using Gwet's Agreement Coefficient (AC1). An AC1 of  $\geq$ = 0.80 will be considered successful concordance between the two measures.

A repeated measures analysis of variance (RM-ANOVA) model will be used to examine the effect of treatment (sonoHSG vs. HSG) on the pain measure. The model will include the order in which the treatments are performed and the interaction between order and treatment. If the interaction is not found to be significant, only the main effects of treatment and order will be analyzed.

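### The primary endpoint declares the two tests interchangeable from a point estimate of an unnamed agreement measure that does not match section 12 and can pass with every occlusion missed

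*Protocol*

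**What the plan says.** Section 10 of the protocol (Primary Study Endpoint) names concordance between the two tests as the primary endpoint and fixes the decision: "The sonoHSG and HSG will be considered interchangeable if the level of agreement between them is >= 80" percent. It does not say which measure of agreement is meant.

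Section 12 (Statistical Analysis) says: "Concordance of the results between sonoHSG and HSG will be calculated using Gwet's Agreement Coefficient" (AC1). It adds that an AC1 of at least "0.80 will be considered successful concordance between the two measures". Section 12 does not use the word interchangeable, and section 10 does not mention AC1. Section 12 lists 95% confidence intervals among the descriptive statistics, but neither success rule uses one.

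The planned size is about 30 women, with a ceiling of 50. The Sample Size Justification in section 8 rests this on feasibility and says "we intend to proceed with a larger clinical trial and appropriately power that study with a larger sample size". Section 4 also describes a feasibility aim: "The specific aim of this study is to evaluate the feasibility of the sonoHSG for it to be determined as the standard of care".

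Other passages give the result more weight. Section 3 says "The results of the study will be significant in determining and possibly changing the standard of care procedure from HSG to sonoHSG". Section 2 says "If sonoHSG proves to be efficacious, our future steps will be to educate referring physicians and patients".

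**The concern.** There are three linked problems.

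1. **Two criteria.** If section 10 means percent agreement, as the percent sign suggests, the same data can pass section 10 and fail section 12. If section 12 is meant to define section 10, the 80% is mislabelled, because AC1 is corrected for chance agreement and is not a percentage of women.
2. **A point estimate.** About 30 women leave a wide interval around any passing value. That is acceptable for deciding whether to go on to a larger trial. It is not acceptable for declaring two diagnostic tests interchangeable when the result is also meant to bear on the standard of care.
3. **One overall figure.** When most women have patent tubes, agreement on patency dominates both percent agreement and AC1. The verdict can then be reached although sonoHSG misses half or all of the occlusions, and missing an occlusion is the error that matters most in a patency test.

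**Working it through.** **Inputs.** The thresholds of 80% (section 10) and AC1 0.80 (section 12) and n = 30 (section 8) come from the protocol. The protocol gives no power calculation to reproduce.

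**Assumptions.** Each woman contributes one binary result, occluded or patent; the protocol does not state the unit. The occlusion rate in this sample is not given either. Section 2 says "approximately 25-35% of female infertility can be attributed to fallopian tube pathology", but that is a share of causes and not a rate in this cohort. Section 7 admits women with non-tubal diagnoses and excludes tubal ligation and salpingectomy. A range of 5% to 35% is therefore shown.

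**Formula.** Let po be the observed proportion agreeing and q the mean of the two tests' proportions occluded. Then pe = 2q(1 − q) and AC1 = (po − pe)/(1 − pe).

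**Step 1: do the two thresholds agree?** At 24/30, po = 0.800. AC1 is highest when no woman is occluded on both tests: the 6 disagreements give q = 6/60 = 0.10, pe = 0.18 and AC1 = 0.62/0.82 = 0.756. It is lowest at q = 0.50: pe = 0.50 and AC1 = 0.30/0.50 = 0.600. Over all 2×2 tables at n = 30:

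| Agreeing | AC1 range | Section 10 as percent | Section 12 |
|---|---|---|---|
| 24/30 | 0.600–0.756 | pass | always fails |
| 25/30 | 0.667–0.803 | pass | depends on table |
| 26/30 | 0.733–0.848 | pass | depends on table |
| 27/30 | 0.800–0.890 | pass | always passes |

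The conflict runs one way only: AC1 never passes when percent agreement fails.

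**Step 2: precision at a pass.** The exact (Clopper–Pearson) 95% CI for 24/30 is 61.4% to 92.3%. For an AC1 of 0.804 (4 women occluded on both tests, 4 on HSG only, 22 patent on both) the 95% CI is about 0.57 to 0.96 by bootstrap and 0.61 to 1.00 by the analytic variance.

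**Step 3: can the rule pass with occlusions missed?**

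- 8 occluded on HSG, 4 missed, no false positives: po = 26/30 = 0.867, q = (8 + 4)/60 = 0.20, pe = 0.32, AC1 = 0.547/0.68 = 0.804. Both readings pass. Occlusions found: 4/8, exact 95% CI 16% to 84%.
- 5 occluded on HSG, all missed, no false positives: po = 25/30 = 0.833, q = 5/60 = 0.083, pe = 0.153, AC1 = 0.681/0.847 = 0.803. Both readings pass. Occlusions found: 0/5, exact 95% CI 0% to 52%.

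**Step 4: how often?** Exact multinomial enumeration at n = 30, no false positives:

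| Occluded | Half missed: AC1 rule passes | All read patent: AC1 rule passes | Half missed: the two readings conflict |
|---|---|---|---|
| 5% | 100% | 99.7% | 0% |
| 10% | 99% | 93% | 1% |
| 15% | 93% | 71% | 6.5% |
| 20% | 80% | 43% | 17% |
| 25% | 62% | 20% | 31% |
| 30% | 43% | 8% | 42% |
| 35% | 26% | 2% | 48% |

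With half of occlusions missed, the true AC1 is 0.973, 0.942, 0.906, 0.866 and 0.820 at 5% to 25% occluded. All of these exceed 0.80, so neither a confidence interval nor a larger sample would by itself expose the misses. At n = 50 the AC1 rule still passes 99.7%, 96% and 84% of the time at 10%, 15% and 20%.

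**The case against.** The strongest reply is that section 12 simply puts section 10 into operation. Both speak of concordance between the same two tests, the cut-off has the same digits, and AC1 is itself called an agreement coefficient. On that reading the first problem is a stray percent sign. This is a fair reading, but the text does not make the link, and a reader who takes 80% literally reaches a different verdict at 24/30.

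The conflict rates in the table also come from a poor test. With sensitivity 0.90 and specificity 0.95 the two readings conflict in only about 1% to 13% of trials over 5% to 35% occluded, and with 0.95 for both in about 1% to 6%. That stands: if sonoHSG works well, the wording conflict is usually small.

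The protocol is open about its sample size, calls the study a pilot and plans descriptive confidence intervals. That also stands, and it is why the small sample and the point-estimate rule are not faulted as the basis for a go-forward decision.

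The missed-occlusion rates depend on an assumed unit and occlusion rate. Counting tubes would give up to 60 results. At 5% occluded only about 1.5 women are affected, so the 100% pass rate there says little. At 25% to 35% a test that reads everyone as patent passes the AC1 rule only 20% to 2% of the time. A SAP may well tabulate results by HSG finding. None of this removes the problem, because section 10 fixes the verdict on the overall figure alone.

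Finally, a table without a pass/fail rule leaves the overall rule able to pass with occlusions missed. That is true. The table is enough only because the interchangeability verdict is dropped at the same time.

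**Conclusion.** The concern holds and should be fixed. Sections 10 and 12 give criteria that are certain to disagree at 24/30 and may disagree at 25/30 and 26/30, unless section 10 is declared to mean AC1. Choosing AC1 for both removes that conflict but not the other two weaknesses. The verdict would still rest on a point estimate with a 95% CI of roughly 0.6 to 1.0 at the threshold, and it could still be reached with 0 of 5 occlusions found.

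The missed-occlusion problem is largest when occlusion is uncommon, which is where the wording conflict is smallest. The sizes rest on one binary result per woman and an assumed 5% to 35% occluded. What is wrong is the stated decision rule and the word it licenses, not the sample size.

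**What to change.** 1. State one criterion in sections 10 and 12, for example by defining the level of agreement in section 10 as AC1 of at least 0.80, and report it with its 95% CI.
2. Replace the interchangeability verdict with a statement that the result supports proceeding to the larger powered trial already planned in section 8. With that wording the point-estimate rule can stay and needs no confidence bound.
3. Report agreement separately among HSG-occluded and HSG-patent results with exact 95% CIs, and read the primary result alongside them. No further pass/fail rule is needed.

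The cost is wording in two sections and one table from results that section 11 already collects. The pilot makes a weaker claim. The interval for the occluded group will be wide, since 30 women at 5% to 35% occluded gives only about 2 to 10 of them.

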#### Secondary Endpoint:

- Quantification of level of patient pain in regard to sonoHSG versus HSG

#### 11. RESEARCH PROCEDURES

- *Include a detailed description of all procedures to be performed on the research subject and the schedule for each procedure.*
- *Include any screening procedures for eligibility and/or baseline diagnostic tests*

- Include procedures being performed to monitor subjects for safety or minimize risks
- *Include information about drug washout periods*
- If drugs or biologics are being administered provide information on dosing and route of administration
- Clearly indicate which procedures are only being conducted for research purposes.
- If any specimens will be used for this research, explain whether they are being collected specifically for research purposes.
- Describe any source records that will be used to collect data about subjects
- Indicate the data to be collected, including long term follow-up

Patients will be presented with the study information at the point of contact at the fertility clinic. They will then be contacted via phone prior to their scheduled appointment. A detailed overview of the study will be presented as well as the consent form. Upon verbal agreement over the phone, the clinician and/or study coordinator will go over the consent process in person on the day of the scheduled visit. As part of this study, subjects will have both the HSG and SonoHSG performed consecutively. The HSG will be performed as part of standard of care and the sonoHSG will be performed as part of research. In order to reduce bias, the procedures will be randomized in REDCap before each subject's scheduled visit. The clinicians will be blinded to the results of each procedure until both procedures have been completed.

The pain scale will be administered verbally immediately after each procedure by the technician/other study personnel in the procedure room.

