#### Data to be collected/obtained

The Data Collection Form will be completed for each enrolled patient. The data collection form contains the following categories of information to be collected/obtained for each subject:

- Patient record demographic data
- Patient record data on pre-existing co-morbid conditions or underlying disease
- Results of HSG and SonoHSG
- Response to evaluation survey with pain scale

The information that links the subject ID with the PHI (the Coded Identifier List) will be kept in the PI's locked office and separate from the Data Collection Forms. Coded data from the Data Collection Form will be collected and stored in a REDCap database. The ultrasound images from the sonoHSG will be stored in the research PACS.

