## Plan for Data Management:

The PI will be responsible for the collection and storage of study data. The research coordinator will assign and record the Subject IDs on the Coded Identifier List. The hardcopy study eligibility forms and data collection forms will be kept in separate, locked file cabinets in the research office. The data elements from the data collection forms and imaging studies will be recorded in REDCap. The ultrasound images from the sonoHSG will be stored in the research PACS. A research report will be issued and kept as part of the research records. This report will be available to the fertility clinicians to incorporate into their clinical report of the HSG but will not be available in the clinical PACS. Study data in these files will be analyzed by our study statistician(s) on computers that will be protected by passwords and active anti-virus software. Laptops, USB flash drives, and/or external hard drives used for data analysis purposes by our study staff will be protected by password, active anti-virus software, and encryption by Northwell standards. Our data analysts do not have access to the link between the study Subject IDs and patient names.

The PI and Co-Investigators are responsible for ensuring proper study documentation to verify compliance with IRB and GCP guidelines. As part of the safety plan for this study, the study staff will review study patient records to ensure that appropriate mechanisms to protect the safety of study participants are being followed, that protocol requirements are being adhered to, and that data are accurate, complete, and secure. Patient records include consent forms, data collection forms, and/or adverse event logs, and medical charts.

At periodic meetings of the study staff, the PI will report on the number of subjects enrolled in the study.

The coordinator will work with study personnel to securely store and record all study data. Only investigators who are listed on the IRB will have access to PHI associated with the study. All study documents will be stored securely on an IRB and HIPAA compliant system, and paper documents will be stored in a locked office.

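### The blind ends when both procedures are completed, not when both tubal results are recorded, so the primary endpoint could use an HSG read made with the sonoHSG result known

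*Protocol*

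**What the plan says.** Section 11 (Research Procedures) gives each subject both tests, one after the other; the Schedule of Events puts both at Visit 1. Two safeguards follow. Order is randomized: "In order to reduce bias, the procedures will be randomized in REDCap". Then the blind: "The clinicians will be blinded to the results of each procedure until both procedures have been completed".

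Section 14 (Plan for Data Management) describes what happens to the sonoHSG findings. The images go to the research PACS. Then: "A research report will be issued and kept as part of the research records", and "This report will be available to the fertility clinicians to incorporate into their clinical report of the HSG". By context this is the sonoHSG report. No time is given relative to the HSG read.

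The endpoint data are described in two places. The data collection form lists "Results of HSG and SonoHSG", and section 14 says "The data elements from the data collection forms and imaging studies will be recorded in REDCap". Neither states who reads, when the read is recorded, or which HSG read counts if there is more than one. Section 6 says that the physicians of both departments "will play the dual role of clinician and research investigator".

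Section 10 attaches a claim to the result: "The sonoHSG and HSG will be considered interchangeable if the level of agreement between them is" 80% or more. Section 12 sets the analysis criterion at Gwet's AC1 of 0.80 or more.

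**The concern.** An agreement statistic measures the tests only if the two reads are independent. If a reader knows one result while forming or finalizing the other, doubtful findings tend to be settled towards the known result. Agreement then rises although neither test has improved. The bias runs towards the conclusion that the protocol hopes to reach: interchangeability in section 10 and, in section 3, a possible change in the standard of care.

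The protocol means to prevent this, but it ties the end of the blind to the wrong event. Completing a procedure and recording its result are different steps. Because the tests are consecutive, on a plain reading the blind can end the same day, before either result has been written down. Section 14 makes this more than loose wording, because it foresees an HSG report written with the sonoHSG findings at hand. Sharing that report for patient care is not a fault. What is missing is a rule that the endpoint read comes first.

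**Working it through.** **Reading the text.** No protocol figure is in dispute; the sample of 30 is justified by feasibility, so there is no calculation to reproduce. The check takes the places that govern blinding, reading, recording and reporting.

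| Question | Where | What the protocol fixes |
|---|---|---|
| When does the blind end? | Section 11 | On completion of both procedures |
| Must a result be recorded first? | Sections 10, 11, 12, 14, 16 | Not stated |
| When is the sonoHSG report released? | Section 14 | No time given |
| Which HSG read enters the endpoint? | Sections 10, 11, 12, 14 | Not stated |
| Are the readers separate? | Section 6 | Not stated; dual roles only |

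The text is therefore compatible with two paths. In one, both results are formed and recorded under the blind, and the report is shared afterwards. In the other, the HSG result is finalized after disclosure, and that version enters the analysis. Nothing excludes the second.

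**How far the second path could move the result.** This is an illustration, and every input except n and the two success criteria is an assumption.

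- n = 30 (section 8), with one normal/abnormal result per patient per test.
- True (blinded) agreement p; abnormal proportion q on both tests; each discordant cell equal to (1 − p)/2.
- A share f of discordant HSG reads is revised to match the sonoHSG.

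Recorded agreement is p + f(1 − p). For p = 0.80 and f = 1/3, this is 0.80 + 0.20/3 = 0.867. The discordant cells are equal, so q does not change, and revising the sonoHSG towards the HSG gives the same table.

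AC1 = (pa − pe)/(1 − pe), with pe = 2π(1 − π) and π the mean abnormal proportion. For q = 0.30, pe = 2 × 0.30 × 0.70 = 0.42. With no revision, AC1 = (0.80 − 0.42)/0.58 = 0.655; with half revised, AC1 = (0.90 − 0.42)/0.58 = 0.828.

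The probabilities below sum the exact multinomial distribution of the 2×2 table over all outcomes that meet each rule: AC1 ≥ 0.80 (section 12), or raw agreement of at least 24 of 30, that is 80% (section 10).

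| Share revised f | 0 | 5% | 10% | 1/3 | 1/2 |
|---|---|---|---|---|---|
| Recorded agreement, p = 0.80 | 0.800 | 0.810 | 0.820 | 0.867 | 0.900 |
| Population AC1, q = 0.30 | 0.655 | 0.672 | 0.690 | 0.770 | 0.828 |
| P(AC1 ≥ 0.80), q = 0.30 | 0.147 | 0.178 | 0.213 | 0.447 | 0.667 |
| Population AC1, q = 0.15 | 0.732 | 0.745 | 0.758 | 0.821 | 0.866 |
| P(AC1 ≥ 0.80), q = 0.15 | 0.287 | 0.328 | 0.373 | 0.622 | 0.802 |
| P(raw ≥ 24/30) | 0.607 | 0.660 | 0.712 | 0.905 | 0.974 |

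**Other levels of true agreement.** With p = 0.70 and q = 0.30, P(AC1 ≥ 0.80) is 0.016, 0.023, 0.033, 0.147 and 0.351 across the same shares; for the raw rule it is 0.160, 0.206, 0.262, 0.607 and 0.847. With p = 0.90 and q = 0.15, P(AC1 ≥ 0.80) is 0.802, 0.849 and 0.935 for f = 0, 10% and 1/3; for the raw rule it is 0.974, 0.985 and 0.997. If the tests truly agree well, revision hardly changes the raw verdict, though AC1 still moves.

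**The case against.** The best case against is that a blind exists and its natural reading already covers the gap. A diagnostic procedure can fairly be called completed once its result is obtained, and tubal patency may well be judged in real time. Section 14 deals with clinical communication: adding the sonoHSG report to the clinicians' HSG report need not mean re-reading the HSG. No section names that clinical report as the endpoint source, and the sonoHSG report is kept out of the clinical PACS. The data collection form or the REDCap build, neither of which is shown, may fix the order of entry. The revision share is assumed, and the study is an unpowered pilot to be followed by a larger trial (section 8).

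Much of this stands, and it limits the claim: the text permits an unblinded endpoint read but does not establish one, nor that one person reads both tests. It does not remove the point. The blinding sentence itself distinguishes results from procedures and ties release to the procedures. A form not shown may happen to help, but it does not change the release rule that the protocol states. Nor can an analysis plan repair this later, because independence cannot be restored to a read already made with the other result known. The pilot status lowers the weight, but section 10 still draws an interchangeability conclusion from the figure.

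**Conclusion.** The concern holds as a gap in the blinding rule that should be fixed. The protocol does not ensure that the two results behind its only primary endpoint are recorded independently, and any resulting bias would favour agreement. The size is unknown. Under the assumed 80% true agreement and 30% abnormal, the chance of meeting the AC1 criterion goes from 0.15 with no revision to 0.18–0.21 at 5–10% revised and 0.45–0.67 at a third to a half. With 15% abnormal the same steps are 0.29, 0.33–0.37 and 0.62–0.80. The effect is therefore nil if reads are kept, modest at low shares, and serious only if a third or more of discordant reads are revised; nothing in the protocol supports or excludes such a share. Confidence is moderate, because it rests on reading completion of a procedure as not including a recorded interpretation.

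**What to change.** Three small edits to the protocol:

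1. Section 11: end the blind when the tubal result of each procedure has been recorded and locked in REDCap, in place of when both procedures are completed.
2. Section 14: state that the sonoHSG research report is released to the fertility clinicians only after the HSG read is locked.
3. Section 10: state that the primary endpoint uses these two locked, blinded reads.

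The cost is one clause and two sentences, a lock step in a REDCap database already in use, and a slightly later report to the clinicians. No extra reader, procedure or patient is needed, and sharing the report for care continues. The change must take effect before reads are made, since it cannot be applied to them afterwards.
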